#### 3.7.2 Assessing Adverse Events

When completing appropriate forms for reporting an AE, the Investigator should assess the AEs as follows:

#### **Reported Term for Adverse Event:**

Individual signs or symptoms, will be recorded AEs, in the absence of a diagnosis. If a diagnosis is available based on the signs or symptoms, the diagnosis, should be recorded as the AE term.

#### **Seriousness of Adverse Event:**

- Serious: The AE meets a criterion of the SAE definition.
- Not Serious: The AE does not meet a criterion of the SAE definition.

#### **Severity of Adverse Event:**

The severity of an AE should be graded as one of the following three grades: mild, moderate or severe. To determine the severity of AEs, refer to "Common Terminology Criteria for Adverse Events (CTCAE)" and categorize Grade 1, Grade 2 and Grade 3 or higher grades of CTCAE³² into mild, moderate and severe, respectively. The investigator should determine the severity, taking into account the general status of the subject, baseline values, outcomes, as well as the severity grade. An AE of Grade 4 or Grade 5 should be assessed whether or not it meets the criteria listed under the SAE definition (see Section 3.7.1).

- Mild: The AE is usually transient and may require only minimal treatment or therapeutic intervention. The AE does not generally interfere with usual activities of daily living.
- Moderate: The AE is usually alleviated with additional specific therapeutic intervention. The AE interferes with usual activities of daily living, causing discomfort but poses no significant or permanent risk of harm to the subject.

• Severe: The AE interrupts usual activities of daily living, or significantly affects clinical status of the subject, or may require intensive therapeutic intervention.

#### Relationship to the Study Drug (Causality) of Adverse Event:

The Investigator's causality assessment is the determination whether there is a reasonable possibility that the IMP caused or contributed to the AE. Generally, the facts (evidence) or arguments to suggest causal relationship should be documented. Factors to be taken into consideration when assessing causality include: subject's underlying and pre-existing conditions, prior/concomitant medications, timing of onset relative to study drug (i.e., JTT-662 or placebo) administration, the known PK characteristics of study drug, the currently-known safety profile of study drug, known class effects of similar mechanism of action drugs, the de-challenge/re-challenge response (if available) and any other information that is considered relevant by the Investigator. Causality will be judged in two categories: "not related" or "related".

- Not Related: Sufficient information exists to indicate that the etiology is clearly related to a cause other than the study drug.
- Related: The AE follows a reasonable temporal sequence from the administration of the study drug; follows a known or expected response pattern to the study drug; is confirmed by improvement on stopping the dosage of the study drug (de-challenge); and cannot be reasonably explained by the participant's clinical state.

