- is a congenital anomaly or birth defect
- is an important medical event

**Note:** Important medical events are events that may not result in death, be life-threatening, or require hospitalization but, may be considered SAEs when, based upon appropriate medical judgment, they may jeopardize the patient or subject or may require medical or surgical intervention to prevent one of the outcomes listed in the definition above. Examples of such important medical events include allergic bronchospasm requiring intensive treatment in an emergency room or at home, blood dyscrasias or convulsions that do not result in hospitalization, or the development of drug dependency or drug abuse.

**Adverse Drug Reaction:** All noxious and unintended responses to an investigational medicinal product (IMP), related to any dose administered.

*Note:* The phrase "responses to a medicinal product" means that a causal relationship between the medicinal product and an AE is at least a reasonable possibility, i.e., the relationship cannot be ruled out.

**Unexpected Adverse Drug Reaction:** An adverse drug reaction (ADR) of which nature (specificity) or severity is not consistent with the applicable product information (e.g., IB).

**Death:** Death represents an outcome and an SAE criterion, not an event term. The medical condition with the fatal outcome should be reported unless the cause of death is unknown, in which case the term "Death" is acceptable.

Inpatient Hospitalization/Prolongation of Hospitalization: Any admission (even if less than 24 hours) to a healthcare facility. Admission also includes transfer within the hospital to an acute/intensive care unit (e.g., medical floor to the coronary care unit). Initial and prolonged hospitalizations that **do not** meet this SAE criterion include those due to social and/or convenience reasons (e.g., lack of personal care at home, unable to transfer to non-acute facility), admission to rehabilitation/hospice/skilled nursing facilities, emergency room visits, same-day/outpatient/ambulatory procedures, and those for pre-planned, elective procedures for a pre-existing condition that did not worsen after the ICF has been signed (no AE recorded). However, if the hospitalization was prolonged due to a complication of a pre-existing condition, the complication (same diagnosis) would qualify as an SAE.

**Disability:** A substantial disruption of a person's ability to conduct normal life functions.

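### Read literally, the two causality definitions in Protocol 3.7.2 leave some adverse events in neither category and conflict with the protocol's own reasonable-possibility standard

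*Protocol*

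**What the plan says.** Protocol 3.7.2, under the relationship to study drug, opens with a general standard. The assessment is "the determination whether there is a reasonable possibility that the IMP caused or contributed to the AE". Among the factors to weigh it lists "the de-challenge/re-challenge response (if available"), so de-challenge is optional there.

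The section then says "Causality will be judged in two categories", with one bullet for each:

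- *Not Related*: "Sufficient information exists to indicate that the etiology is clearly related to a cause other than the study drug".
- *Related*: four elements separated by semicolons and closed by a single conjunction. The AE has reasonable timing, fits a known or expected pattern, "is confirmed by improvement on stopping the dosage of the study drug (de-challenge); and cannot be reasonably explained by the" participant's clinical state.

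Protocol 3.7.1 defines an adverse drug reaction by a causal link that is "at least a reasonable possibility, i.e., the relationship cannot be ruled out". It also defines an unexpected reaction, one "of which nature (specificity) or severity is not consistent with the applicable product information". Protocol 3.7.3 provides for reporting of suspected unexpected serious reactions.

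**The concern.** The two bullets are not complements. One demands a clear alternative cause, and the other demands four simultaneous conditions, one of which can be observed only after the drug has been stopped. An investigator who follows the bullets has no valid entry for an AE that lies between them, and the documents do not say whether the lead-in or the bullets prevail.

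Four parts of the plan use the recorded call:

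- **Criterion 2 in Protocol 3.5** counts severe non-serious AEs considered related, in two subjects of the same cohort. On the literal bullet it could count only AEs in subjects whose dosing had already been interrupted, withdrawn or completed. That is awkward for a rule meant to decide whether dosing should stop.
- **The late-SAE rule in Protocol 3.7.3** requires a report after the collection window only if the Investigator considers the SAE related.
- **Follow-up under the outcome categories in Protocol 3.7.2** continues all related AEs until the clinical outcome is known.
- **SAP 6.10.1** counts drug-related TEAEs in the overview and tabulates TEAEs by causality.

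Protocol 3.7.3 also asks for a causality call before the first SAE report is sent, even on minimal information. At that point the de-challenge result will often be unknown, and the evidence that *Not Related* requires may be missing too.

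**Working it through.** There is no planned figure to reproduce. The check is of the wording.

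**1. The definitions as conditions.** Let T = reasonable timing, P = known or expected pattern, D = improvement confirmed on stopping the drug, E = not explained by clinical state, and C = clear other cause.

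- *Related* = T and P and D and E
- *Not Related* = C

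The two cover every AE only if the absence of C guarantees all of T, P, D and E. Nothing in the text makes that so.

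**2. How the gap arises.** Take AEs with no clear other cause (C false) that clinical state does not explain (E true). T, P and D then give 2^3 = 8 combinations. One is *Related*, and 8 - 1 = 7 fit neither category. This counts logical combinations. It says nothing about how many AEs would fall in them.

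**3. Cases, assuming no clear other cause.**

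| Case | Condition not met | Fits a bullet? |
|---|---|---|
| Severe non-serious AE, plausible timing, resolves with dose unchanged | D | Neither |
| Fatal AE | D | Neither |
| Reaction that fits no known or expected pattern | P | Neither |
| SAE with new onset after the collection window | D (no dosing left to stop) | Neither |
| AE that lasts to the final dose on Day 28, then improves | none, if T, P and E hold | *Related* |
| Reaction unexpected only in severity | none, if T, D and E hold | *Related* |

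The last two rows show that unchanged dosing, or being unexpected in the sense of 3.7.1, does not by itself exclude *Related*.

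**4. Against the protocol's own standard.** Under the lead-in of 3.7.2 and the drug-reaction definition in 3.7.1, each of the first four cases could be called related, because a link has not been ruled out. De-challenge is a factor to use when available in the lead-in and a requirement in the bullet. The same event can therefore receive different answers within one section.

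**5. Which uses are exposed.** Criterion 1 in 3.5 is partly protected: it names a serious adverse drug reaction, which 3.7.1 defines by the broader standard. Criterion 2 has no such anchor and rests on the recorded call, as do the late-SAE rule and the causality tables.

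**The case against.** The strongest reply is that the lead-in already states the standard and the bullets merely describe typical cases under it. An investigator forced to choose might also default to *Related*, because *Not Related* needs positive evidence of another cause. That is a reasonable reading, and it is why the direction of any error is unknown. It does not settle the matter, because the bullets define the categories to be recorded and nothing ranks the lead-in above them.

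Three stronger readings are tempting, and the documents do not support them:

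- **That many ordinary AEs would be misclassified.** No AE frequencies are given. The count of 7 in 8 is not a rate.
- **That mild AEs weaken the suspension rules.** The protocol says of a mild AE: "The AE is usually transient and may require only minimal treatment or therapeutic intervention". Such AEs may resolve on drug and fall in the gap, but they cannot meet either criterion in 3.5, which require a serious reaction or severe AEs. For them the effect is mainly on the causality tables.
- **That no unexpected reaction can be related, so expedited reporting is blocked.** Section 3.7.1 judges expectedness against product information. The pattern in the *Related* bullet is not tied to that source, and the lead-in admits known class effects. Section 3.7.3 does not say that the Sponsor's reporting depends on these bullets.

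Safeguards also stand. All AEs are recorded whatever the causality, and SAEs within the window are reported regardless. Section 3.7.1 requires follow-up of any AE until it is resolved or stable. Actions under 3.5 depend on joint review by the Investigator, Medical Monitor and Sponsor, and the Sponsor may suspend for any reason. The Cohort 3 review in 1.3 and 3.2 is not limited to related AEs. TEAE tables by severity, regardless of causality, are planned. There is one site. CRF guidance and the separate SAE instructions are not among the documents and may already resolve the wording.

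**Conclusion.** The inconsistency is real and should be corrected. Two categories are offered, their definitions do not cover all AEs, and the *Related* bullet is stricter than the standard stated just above it and in 3.7.1. This is a stated rule that goes wrong if followed as written, rather than a missing detail.

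Its practical size cannot be estimated, for want of AE frequencies and any statement of how investigators would resolve the conflict. The exposure is confined to criterion 2 in 3.5, late SAE reporting, follow-up of related AEs and the drug-related and causality tables. The safeguards above make it a modest problem, and no decision in the trial is shown to be affected.

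The conclusion assumes that the semicolons and the closing conjunction mean that all four conditions are required, and that no document outside the protocol overrides the bullets.

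**What to change.** Replace the two bullets with complements built on the standard already in the protocol:

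- *Related*: a causal contribution of the study drug is a reasonable possibility, meaning that it cannot be ruled out.
- *Not Related*: there is no such reasonable possibility.

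Keep timing, known or expected pattern, de-challenge where available, and clinical state as factors to consider, none of them mandatory. State that related in both criteria of 3.5 and in the late-SAE rule of 3.7.3 uses this definition, and align the CRF completion guidance. The SAP needs no change, since its tables use the recorded call.

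No new data are needed. There are three costs. Protocol 4.1 requires written IRB approval before an amendment is implemented. Compared with the literal bullet, some more AEs may be classed as related. The definition must also be the same for all cohorts: if the change is made mid-study, for instance between Cohorts 1 and 2 and Cohort 3, AEs already recorded should be re-assessed under it so that one table does not mix two definitions across dose groups.

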#### **Action Taken with Regard to Study Drug:**

- Dose Not Changed: The subject was on treatment with the study drug when the AE occurred, and the study drug dosing was maintained at the same dose level.
- Drug Interrupted: The subject was on treatment with the study drug when the AE occurred, and the study drug dosing was temporarily discontinued and then re-started.
- Drug Withdrawn: The subject was on treatment with the study drug when the AE occurred, and the study drug dosing was permanently discontinued.
- Not Applicable: The subject was not receiving treatment with the study drug when the AE occurred (i.e., AE occurred before placebo dosing on Day -1 or after the last study drug administration), or if the subject died.

#### **Outcome of Adverse Event:**

One outcome should be recorded for each AE and the outcome of each AE should be classified as follows:

- Not Recovered/Not Resolved: The subject has not yet recovered from the AE; the event has not improved (follow-up of all SAEs and all related AEs will be continued until the overall clinical outcome is ascertained).
- Recovering/Resolving: The subject has not yet recovered from the AE, however, the event is improving (follow-up of all SAEs and all related AEs will be continued until the overall clinical outcome is ascertained).
- Recovered/Resolved: The subject recovered from the AE with no sequelae.
- Recovered/Resolved with Sequelae: The subject recovered from the AE with sequelae.
- Fatal: The subject's death was a result of the AE.

#### Start Date and Time, and End Date and Time of Adverse Event:

The start date and time of each AE with an onset time during the period for AE assessment should be recorded. The end date and time of each AE should be recorded in the following manner:

- If the outcome of AE is "Recovered/Resolved" or "Recovered/Resolved with Sequelae", record the date and time of the AE outcome.
- If the outcome of AE is "Fatal," record the date of the death.
- If the outcome of AE is "Recovering/Resolving" or "Not recovered/Not resolved", the end date and time of the AE outcome should NOT be recorded.

For AEs related to abnormalities in parameters such as vital signs, ECGs, record the date/time when the test was performed as the start date/time and end date/time. For AEs related to abnormalities in laboratory values, record the date/time when the sample was collected for the test as the start date/time and end date/time.

If an identical AE occurs repeatedly in a subject, the Investigator (or designee) should judge whether it is a single event or a composite of more than one event considering the features, frequency and severity of the AE from a medical perspective.

#### 3.7.3 Reporting Adverse Events

#### **Adverse Events Reporting:**

Adverse events occurring (initial occurrence or a worsening of a pre-existing condition) after the ICF has been signed and up to the day when the decision to screen fail the subject is made (for screen failure subjects), up to 7 days (for subjects discontinuing the study after dosing on Day -1, but before dosing on Day 1) or 14 days (for subjects discontinuing the study after dosing on Day 1) after the last dose of study drug will be reported and entered in the CRFs. Conditions detected prior to the ICF signature should be documented as medical history. Other conditions identified between the ICF signature and Day 1 (prior to dosing) could be included in the medical history, based on the Investigator's medical and scientific judgement. For guidance, refer to Section 3.6.7.5 of the protocol.

Adverse events will be reported on the AE CRF page.

When a subject withdraws from the study due to a non-serious AE, whether or not related to study drug, the Investigator must notify Akros within 24 hours of the study center being informed of the withdrawal.

#### **Serious Adverse Event Reporting:**

#### Reporting by Investigator

Detailed instructions regarding SAE reporting will be provided in the appropriate documents outside of this protocol. A brief, non-all-inclusive summary is provided below.

Any SAE experienced by a study subject after signing the informed consent up to the day when the decision to screen fail the subject is made (for screen failure subjects), 7 days (for subjects discontinuing the study after dosing on Day -1, but before dosing on Day 1) or 14 days (for subjects

discontinuing the study after dosing on Day 1) after the last dose of study drug will be reported to the Sponsor or designee. Additionally, SAEs that occur after this period will also be reported to The Sponsor or designee, if the Investigator considers the SAE related to the study drug.

Serious AEs (both initial reports and follow-up information) must be reported to the Sponsor or designee within 24 hours of the Investigator's (site's) awareness or notification of the event.

The Investigators should make every effort to provide complete information when reporting the SAE (both for initial reports, as well as for follow-ups).

**Notes**: The Investigator should make every effort to assess the causality of the SAE prior to transmission of the initial SAE report, even if the Investigator has minimal information. The SAE report should be amended, if the Investigator changes his/her opinion of causality based on the follow-up information.

Personal information that could potentially identify the subject MUST NOT be included in any document that is sent to Sponsor or designee as per ICH GCP Principles 2.11 and other applicable laws and legislations.

The Investigator must continue to follow the subject until the SAE has subsided, the condition becomes chronic in nature, the condition stabilizes (in case of persistent impairment), or the subject dies. Within 24 hours of receipt of follow-up information, the Investigator must submit it to the Sponsor or designee.

The Investigator is also required to submit SAE reports to the IRB, in accordance with local requirements. The Investigator will receive all Suspected Unexpected Serious Adverse Reaction (SUSAR) reports for onward submission to their local IRB, as required.

#### Reporting by the Sponsor

Competent authorities will be informed by the Sponsor or designee of SUSARs.

#### Exposure in Utero Reporting:

If a female subject or a female partner of a male subject participating in the study becomes pregnant after the subject receives study drug on Day 1 and up to 30 days after the last dose of study drug, the Investigator should report the pregnancy to the Sponsor or designee within 24 hours of being notified. To report the pregnancy, the site must complete the Exposure *in Utero* Form which is provided separately to the Investigator.

The female subject or the female partner of a male subject should be followed by the Investigator until completion of the pregnancy if the subject received active (i.e., JTT-662) treatment. If the pregnancy ends for any reason before the anticipated date, the Investigator should notify the Sponsor or designee. At the completion of the pregnancy, the Investigator should document the outcome of the pregnancy. If the outcome of the pregnancy meets the criteria for immediate classification as an SAE (i.e., spontaneous abortion, stillbirth, neonatal death or congenital anomaly), the Investigator should follow the procedures for reporting an SAE as described above.

#### **Overdose Reporting:**

An overdose is a significant variation from the recommended/scheduled dosage for a product. For the purposes of this study, overdose is defined as any confirmed use of study drug more than indicated by the protocol. Information on overdose in subjects is collected by the Sponsor or designee, *via* a separate form provided to the Investigator. If a subject experiences an overdose during the course of the study, the Investigator or qualified designee must report it to the Sponsor or the designee as soon as possible after he/she first becomes aware of it. If any overdose leads to an AE or SAE, the AE should be documented and the SAE should be reported to the Sponsor or designee, as described under the SAE reporting section.

#### 3.8 Identification of Treatments

#### 3.8.1 Method of Assigning Subjects to Treatment Groups

After signing the ICF, potential study subjects will be assigned a screening number (XXX) consecutively. The screening number will be used throughout the study. Following confirmation of eligibility on Day 1, the pharmacist at the site will assign a four digit randomization number XXYY, where XX represents the cohort number (beginning with 01) and YY represents a consecutively assigned number beginning with 01 ending with 12 in each cohort. Subjects that took placebo on Day -1 but are not randomized into Cohort 1 on Day 1, Hour 0 can be randomized into Cohort 2 on the same day, if still eligible, and will be assigned a randomization number XXYY where XX represents the cohort number (beginning with 02) and YY represents a consecutively assigned number.

To ensure an adequate number of evaluable subjects, replacement subjects may be enrolled in the study at the discretion of the Sponsor, as appropriate. Each replacement subject will be assigned the same treatment as the subject that is being replaced. The first digit in the randomization number of the replacement subject will be five (i.e., the replacement subject for the first subject [0101], becomes 5101).

